5.4.3.1.1. Preparation

MIRV is an experimental anticancer drug, and, as with other potentially toxic compounds, caution should be exercised when handling this compound. It is recommended that gloves and protective garments be worn during preparation. The desired amount of drug should be withdrawn from the vial(s) and diluted using 5% dextrose to a final concentration as outlined in the Pharmacy Manual.

Note: MIRV is incompatible with saline (0.9% sodium chloride). Therefore, dilutions should be made using 5% dextrose. Infusion bags must be labeled with the protocol number, patient number, storage temperature, dose, and volume of MIRV filtered into the bag, or labeled according to institutional protocol. Once the solution is prepared, the infusion bag should be stored at room temperature protected from direct sunlight, and the infusion must be completed within eight hours of preparation. Please refer to Pharmacy Manual for further details.

If necessary, MIRV from different drug lots may be mixed in a single-dose administration.

5.4.3.1.2. Administration

MIRV is administered at 6 mg/kg AIBW as an IV infusion following preparation as outlined in the Pharmacy Manual. Details on required and compatible infusion materials are also included in the Pharmacy Manual.

At C1D1 MIRV should be administered at a rate of 1 mg/min; after 30 min, the rate can be increased to 3 mg/min if well tolerated. If well tolerated after 30 min at 3 mg/min, the MIRV infusion rate may be increased to 5 mg/min. Subsequent infusions may be delivered at the tolerated rate. Therefore, the overall length of infusion will vary depending on dose and patient tolerability. After infusion, the IV line should be flushed with 5% dextrose as needed (PRN) to ensure delivery of the full dose.

Patients will be carefully observed during each infusion and vital signs are taken as outlined in the Schedule of Assessments (Table 2). Patients will remain in the clinic under observation for four hours after the first infusion, and for at least one hour after each subsequent infusion. While in the treatment area, patients are closely monitored for AEs.

5.5. Dose Modification Guidelines

Detailed MIRV dose modification guidelines are described below.

5.5.1. Treatment Criteria

In the absence of a TEAE that requires dose modification (as specified in the management guidance for a particular toxicity, see Section 5.5.1.1), a patient must meet the following criteria to receive MIRV at any cycle:

- ANC must be $\geq 1.5 \times 10^9/L$ (1,500/ μ L)
- Platelet count must be $\geq 100 \times 10^9/L$ (100,000/ μ L)
- All non-hematologic toxicities for which a causal association to study drug cannot be ruled out, must be \leq Grade 2 or returned to baseline; the exceptions to this rule being:
 - Treatment-emergent ocular disorders, which must have recovered to \leq Grade 1 or baseline
 - Treatment emergent pneumonitis which must have recovered to \leq Grade 1

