- ^f ECOG, PE, pregnancy test for WCBP, and hematology and chemistry labs (if all parameters are within normal range) do not need to be repeated at C1D1 if performed within the previous 4 days during Screening.
- ^g Vital signs (BP and body temperature) will be measured before start of infusion; post infusion vital signs should be collected as clinically indicated for potential infusion-related reaction.
- ^h Hematology and chemistry labs may be performed up to 4 days prior to D1 of each cycle, and as clinically indicated while on treatment, with results reviewed before each MIRV administration. In the event of severe toxicity, laboratory tests must be repeated as clinically necessary until the toxicity resolves or stabilizes to baseline level.
- ⁱ For women of childbearing potential (WCBP), a urine or serum pregnancy test must be performed within the 4 days prior to D1 of each cycle, and at the 30-Day Follow-up visit. It is recommended to perform monthly pregnancy tests for 3 months after the last dose of MIRV. Additional testing may be performed in accordance with institutional requirements or local regulation.
- ^j Baseline ophthalmic exams will be performed by an ophthalmologist within 14 days before C1D1 and will include the following: visual acuity (with/without corrective lens; whichever best reflects the patient's usual functioning), slit lamp examination, intraocular pressure measurement, and indirect fundoscopy. All patients who have an ophthalmic exam on study treatment (post-baseline) due to emergence of visual signs or symptoms will have a complete ophthalmological examination performed at EOT visit or 30-Day Follow-up visit.
- ^k Ocular symptoms assessment will be performed by the treating physician or other qualified individual before the start of each cycle. For patients reporting > CTCAE Grade 1 ocular symptoms, treatment will be held until the patient is evaluated by an ophthalmologist for a complete examination.
- ^l Radiologic tumor assessment by CT/MRI scan. The same method of radiographic assessment used at Screening must be used at all subsequent radiographic assessments.

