5.5.1.1. Mirvetuximab Soravtansine-Related Adverse Events

Dose modifications for MIRV-related AEs are described in [Table 3](#).

Table 3: Dose Modifications for Mirvetuximab Soravtansine-Related Adverse Events

Severity Grade (CTCAE v5.0)	Dose Modifications for MIRV ^a
Hematological	
Neutropenia	
Grade 2 and Grade 3	Hold drug until ANC is $\geq 1.5 \times 10^9/L$ (1500 / μ L) and resume at the same dose level
Grade 4	Hold drug until ANC is $\geq 1.5 \times 10^9/L$ (1500 / μ L) and then resume at one lower dose level
Febrile neutropenia Grade 3 or 4 (with a single temperature reading $\geq 38.3^\circ C$ or a sustained temperature of $> 38^\circ C$ for > 1 hour)	Hold drug until ANC is $\geq 1.5 \times 10^9/L$ (1500 / μ L) and then resume at one lower dose level
Thrombocytopenia	
Grade 2 and Grade 3	Hold drug until PLT count is $\geq 100 \times 10^9/L$ (100,000/ μ L) and resume at same dose level
Grade 3 associated with clinically significant bleeding that requires transfusion therapy and Grade 4	Hold drug until PLT count is $\geq 100 \times 10^9/L$ (100,000/ μ L) and then resume at one lower level
Non-hematological	
Nausea and Vomiting	
Grade 3 (despite use of optimal antiemetics)	Hold drug until resolved to \leq Grade 1, then resume at one lower level
Grade 4	Permanently discontinue
Diarrhea	
Grade 3 (despite use of optimal anti-diarrheal treatment)	Hold drug until resolved to \leq Grade 1, then resume at one lower level
Grade 4	Permanently discontinue
Ocular Disorders	Refer to Section 5.5.2
Noninfectious Pneumonitis	Refer to Section 5.5.3
Infusion-related Reactions	Refer to Section 5.5.5

Table 3: Dose Modifications for Mirvetuximab Soravtansine-Related Adverse Events (Continued)

Severity Grade (CTCAE v5.0)	Dose Modifications for MIRV ^a
All Other Non-hematological Toxicities (except AEs related to underlying disease, Grade 3 fatigue, isolated symptomatic Grade 3 biochemistry laboratory abnormalities that last for < 7 days including electrolyte abnormalities that respond to medical intervention)	
Grade 3	Hold drug until resolved to ≤ Grade 1, then resume at one lower level For any Grade 3 hepatic toxicity that does not resolve to baseline within seven days, an abdominal CT scan must be performed to assess whether it is related to disease progression.
≥ Grade 3 Cardiac events (excluding Grade 3 hypertension)	Permanently discontinue
Grade 4 non-hematological toxicities	Permanently discontinue

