5.5.2.1. Monitoring and Preventive Measures

In early dose escalation of Study 0401, a relationship was observed between MIRV plasma exposure and likelihood of an ocular event and response. Exposure-response modeling suggested that a dose of 6.0 mg/kg AIBW provided adequate exposure for response while also maintaining overall exposure within a range that decreased the potential for ocular AEs. Due to the observation of ocular disorders consistent with reversible keratopathy/corneal epitheliopathy in patients treated with MIRV, ocular function will be carefully monitored. Ocular symptom assessments will be performed at baseline and at Day 1 of every cycle thereafter ([Table 2](#)). Complete ophthalmologic exams will be performed in all patients at baseline and every other cycle thereafter if there is a TEAE reported.

Patients are advised to avoid using contact lenses while on MIRV. Baby shampoo and a soft cloth should be used to clean the eyes, and a warm compress at bedtime may be used to decrease any possible inflammation on the eyelid's surface. Please refer to [Section 5.4.2.1](#) and [Section 5.4.2.2](#) for details on the prophylactic use of steroid eye drops and lubricating artificial tears. The use of UVA/UVB sunglasses is recommended in full daylight during the study. The use of temporary lower punctal plugs to increase lubrication of the eyes is optional if lubricating artificial tears and corticosteroid eye drops are not sufficient. If patients report signs or symptoms of ocular disorders, including, but not limited to, blurred vision or eye irritation, the management and dose modification guidelines outlined in [Table 5](#) should be followed.

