5.5.2.2. Management and Dose Modification Guidelines

If a patient develops ocular symptoms of any grade, the patient is required to have a complete examination by an ophthalmologist. If a patient develops \geq CTCAE Grade 2 ocular symptoms, treatment with MIRV must be interrupted. Treatment should not be interrupted solely for Grade 2 ocular signs (eg, Grade 2 keratopathy) unless they are also associated with Grade 2 ocular symptoms. Treatment with MIRV may resume if ocular symptoms improve to Grade 1 or baseline within 28 days of the next scheduled MIRV dose (refer to [Table 5](#) for details). If ocular

symptoms last longer than 28 days, resumption of MIRV, with or without dose reduction, may be considered for those patients who have experienced clinical benefit if agreed upon between the Sponsor and the Investigator. Subsequent eye examinations will be scheduled to occur in every other cycle going forward, from the time that the AE was initially reported, and at either the EOT visit or 30-Day Follow-up Visit after treatment discontinuation, even if the results of the patient’s ocular exam shows no obvious clinical findings. Management of treatment-emergent ocular AEs with inflammatory characteristics should include corticosteroid eye drops and/or other measures as indicated by an ophthalmologist.

Table 5: Management of Ocular Symptoms

Severity Grade (CTCAE v5.0)	Management	Guidelines for MIRV Dose Modifications
Grade 1	Complete eye exam as outlined in Schedule of Assessments (Table 2) Monitor for worsening symptoms	Continue MIRV dosing
Grade 2	Complete eye exam as outlined in Schedule of Assessments (Table 2) Repeat complete exam as clinically indicated Patients should have weekly symptomatic ocular assessments by the Investigator until the symptoms resolve to Grade 1 or baseline or are deemed to be irreversible by the Investigator	Hold MIRV dosing until AE has resolved to Grade 1 or better Patients with ocular symptoms lasting < 14 days may be allowed to resume MIRV at the same dose level Patients with ocular symptoms lasting ≥ 14 days but no more than 28 days may resume MIRV at one lower dose level Recurrence of Grade 2 toxicity on subsequent cycles despite best supportive care will require a MIRV dose reduction of one dose level

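### Protocol 5.5.1 and 5.5.2.2 give opposite dosing instructions for Grade 2 ocular signs without Grade 2 symptoms; a lesser point is that the 28-day limit has no single start point

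*Protocol*

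**What the plan says.** **Signs and symptoms.** Protocol 5.5.1 lists what a patient must satisfy for dosing at each cycle, "In the absence of a TEAE that requires dose modification". Non-hematologic toxicities that may be drug-related must be no worse than Grade 2 or back to baseline, "the exceptions to this rule being" two stricter ones. The first of these is "Treatment-emergent ocular disorders, which must have recovered to" Grade 1 or below, or baseline.

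In Table 3 (5.5.1.1) the ocular row says only "Refer to Section 5.5.2". Section 5.5.2.1 sends patients who report signs or symptoms of ocular disorders to Table 5. Section 5.5.2.2 requires interruption for symptoms of Grade 2 or worse, and then states: "Treatment should not be interrupted solely for Grade 2 ocular signs (eg, Grade 2 keratopathy", in parentheses) "unless they are also associated with Grade 2 ocular symptoms". Table 2 footnote k also words the hold by symptoms above Grade 1: "ocular symptoms, treatment will be held until the patient is evaluated by an ophthalmologist". Section 7.9.1 does the same.

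**The 28-day limit.** For symptomatic patients, 5.5.2.2 first allows resumption if symptoms improve to Grade 1 or baseline by a limit of 28 days tied to the next scheduled dose, and refers to Table 5 for details. Its next sentence concerns symptoms that last more than 28 days. Resumption may then be considered, with or without dose reduction, for patients with clinical benefit if Sponsor and Investigator agree. The Grade 2 row of Table 5 uses symptom duration (under 14 days, or 14 to 28 days). The Grade 3 row gives 28 days with no start point.

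**The concern.** For one identifiable type of patient, the two sections lead to opposite actions on dosing day: a dose withheld or a dose given. Two sites that each follow the protocol as written could treat the same finding differently.

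The case can arise in practice. Section 5.5.2.2 requires a full ophthalmologic examination for ocular symptoms of any grade, and further examinations every other cycle. A patient with only Grade 1 symptoms will therefore be examined for signs.

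The statistical consequence lies in the safety output. SAP 6.2 plans tables of ocular TEAEs leading to dose delay and to dose reduction. If sites apply different rules, those counts reflect how each site read the protocol as well as tolerability.

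**Working it through.** There is no stated figure to reproduce. Part (a) is a comparison of text. Part (b) needs only simple arithmetic.

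**(a) Signs versus symptoms**

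1. *Does the 5.5.1 condition cover signs?* Section 5.5.2.1 speaks of the "observation of ocular disorders consistent with reversible keratopathy/corneal epitheliopathy", and later refers to signs or symptoms of ocular disorders. The term is not limited to symptoms.
2. *Does the opening clause of 5.5.1 take this patient out of the list?* The list applies when no TEAE requires dose modification. Under 5.5.2.2 a Grade 2 sign without Grade 2 symptoms calls for no interruption, so the patient stays within the list.
3. *Is the ocular condition just a general default?* No. It is a named exception, stricter than the Grade 2 limit for other non-hematologic toxicities.
4. *Apply both sections, taking a baseline below Grade 2:*

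| Signs | Symptoms | 5.5.1 | 5.5.2.2 |
|---|---|---|---|
| Grade 1 or below | Grade 1 or below | condition met | no interruption |
| Grade 2 | Grade 2 | condition not met | interrupt |
| Grade 2 | below Grade 2 | condition not met | do not interrupt |

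Of these three cases, only the last is in conflict.

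**(b) The 28-day limit, symptomatic patients only**

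Inputs: 21-day cycle (Protocol 4.1.2) and 28 days (5.5.2.2 and Table 5).

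Assumptions: the dose-anchored limit runs to 28 days after the date the next dose is due, and symptom duration is counted from onset. The documents state neither.

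Let k be the number of days from onset to the next scheduled dose, from 0 to 21.

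- Longest symptom duration under the dose-anchored sentence: k + 28 days.
- Longest symptom duration under the duration sentence: 28 days.
- Difference: (k + 28) − 28 = k days.

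| k | Dose-anchored limit (days of symptoms) | Duration limit | Difference |
|---|---|---|---|
| 0 | 28 | 28 | 0 |
| 7 | 35 | 28 | 7 |
| 14 | 42 | 28 | 14 |
| 21 | 49 | 28 | 21 |

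Example: symptoms start 14 days before the due dose and improve after 35 days. That is 35 − 14 = 21 days after the due date, inside the first limit. But 35 exceeds 28, so the next sentence requires clinical benefit and Sponsor-Investigator agreement.

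**The case against.** **On (a).** The best defence is that the specific guidance governs. Table 3 sends ocular disorders to 5.5.2, and 5.5.2.1 sends reported signs or symptoms to Table 5, which is titled for symptoms. Table 2 footnote k and 7.9.1 also word the hold by symptoms. Section 5.5.2.2 names the very case in dispute. The wording about recovery in 5.5.1 could also be read as applying only to a return after a hold.

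Much of this stands. A reader who follows the pointers reaches an express answer, so it would be wrong to infer that the protocol contains two unconnected ocular regimes. What remains is that 5.5.1 applies its list to dosing at any cycle, in mandatory terms, and nothing lifts its ocular condition. A pointer to another section is not a statement of precedence.

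**On (b).** The dose-anchored sentence itself refers to Table 5, and the Grade 2 row there uses symptom duration. For Grade 2 this leaves loose wording more than two rival rules, which is why (b) is the lesser point. The pointer does not fix when duration starts, and it does not help with Grade 3, whose row gives no start point.

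**Stronger readings that the documents do not support**

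- *That the two limits nearly always disagree in practice.* The arithmetic gives a difference for almost every onset day, but that follows from the assumed calendar. The limits matter only when symptoms last beyond 28 days and then improve before the later limit.
- *That (b) bars some patients from resuming.* It does not. Section 5.5.2.2 still allows resumption by the agreement route.
- *That the 21-day retreatment limit in the Table 3 footnote and 5.5.6 is a third conflict.* It carries an exception for toxicities with their own guidance.
- *That the primary analysis is compromised.* Nothing in the ORR sample size or test depends on these rules.

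**Conclusion.** Part (a) is a real contradiction of limited extent. It concerns patients whose ocular signs are Grade 2 (and above baseline) while symptoms are below Grade 2. No frequency for such findings is given, so the number affected cannot be estimated.

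Part (b) is a wording defect. Under the assumptions stated, the limits differ by 0 to 21 days depending on onset. The size would change if duration were counted from reaching Grade 2 or from the hold. The consequence is whether resumption needs clinical benefit and Sponsor-Investigator agreement. Its frequency is also unknown.

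Together they affect consistency of dosing across sites and the interpretation of descriptive safety tables. The point should be corrected because it concerns hold-or-give instructions for a monitored toxicity, and correction is cheap.

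**What to change.** The sponsor should reconcile Protocol 5.5.1, 5.5.2.2 and Table 5 so that a single criterion governs dosing for ocular signs and symptoms. It should also state one start point for the 28 days, used alike in the 5.5.2.2 text and in the Grade 2 and Grade 3 rows of Table 5. Which criterion and which start point apply are clinical decisions for the sponsor, and none is proposed here.

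The cost is a protocol clarification, by amendment or letter to sites. There is no statistical cost: sample size, alpha and the ORR analysis are unchanged.

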5.5.1.1. Mirvetuximab Soravtansine-Related Adverse Events

Dose modifications for MIRV-related AEs are described in [Table 3](#).

Table 3: Dose Modifications for Mirvetuximab Soravtansine-Related Adverse Events

Severity Grade (CTCAE v5.0)	Dose Modifications for MIRV ^a
Hematological	
Neutropenia	
Grade 2 and Grade 3	Hold drug until ANC is $\geq 1.5 \times 10^9/L$ (1500 / μ L) and resume at the same dose level
Grade 4	Hold drug until ANC is $\geq 1.5 \times 10^9/L$ (1500 / μ L) and then resume at one lower dose level
Febrile neutropenia Grade 3 or 4 (with a single temperature reading $\geq 38.3^\circ C$ or a sustained temperature of $> 38^\circ C$ for > 1 hour)	Hold drug until ANC is $\geq 1.5 \times 10^9/L$ (1500 / μ L) and then resume at one lower dose level
Thrombocytopenia	
Grade 2 and Grade 3	Hold drug until PLT count is $\geq 100 \times 10^9/L$ (100,000/ μ L) and resume at same dose level
Grade 3 associated with clinically significant bleeding that requires transfusion therapy and Grade 4	Hold drug until PLT count is $\geq 100 \times 10^9/L$ (100,000/ μ L) and then resume at one lower level
Non-hematological	
Nausea and Vomiting	
Grade 3 (despite use of optimal antiemetics)	Hold drug until resolved to \leq Grade 1, then resume at one lower level
Grade 4	Permanently discontinue
Diarrhea	
Grade 3 (despite use of optimal anti-diarrheal treatment)	Hold drug until resolved to \leq Grade 1, then resume at one lower level
Grade 4	Permanently discontinue
Ocular Disorders	Refer to Section 5.5.2
Noninfectious Pneumonitis	Refer to Section 5.5.3
Infusion-related Reactions	Refer to Section 5.5.5

Table 3: Dose Modifications for Mirvetuximab Soravtansine-Related Adverse Events (Continued)

Severity Grade (CTCAE v5.0)	Dose Modifications for MIRV ^a
All Other Non-hematological Toxicities (except AEs related to underlying disease, Grade 3 fatigue, isolated symptomatic Grade 3 biochemistry laboratory abnormalities that last for < 7 days including electrolyte abnormalities that respond to medical intervention)	
Grade 3	Hold drug until resolved to ≤ Grade 1, then resume at one lower level For any Grade 3 hepatic toxicity that does not resolve to baseline within seven days, an abdominal CT scan must be performed to assess whether it is related to disease progression.
≥ Grade 3 Cardiac events (excluding Grade 3 hypertension)	Permanently discontinue
Grade 4 non-hematological toxicities	Permanently discontinue

Abbreviations: CTCAE = common terminology criteria for adverse events; ANC = absolute neutrophil count; PLT = platelets; CT = computed tomography; AE = adverse event.

^a Failure to meet retreatment criteria within 1 cycle (21 days) after the missed dose due to insufficient recovery from a treatment-related toxicity will result in treatment discontinuation unless otherwise specified in the management guidance for a particular toxicity.

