5.5.1.2. Mirvetuximab Soravtansine Dose Reduction Dose Levels

MIRV dose reduction will be as described in [Table 4](#).

Table 4: Mirvetuximab Soravtansine Dose Reduction Dose Levels

If the patient was receiving MIRV at:	Dose should be reduced to:
6.0 mg/kg AIBW	5.0 mg/kg AIBW
5.0 mg/kg AIBW	4.0 mg/kg AIBW
4.0 mg/kg AIBW	Permanently discontinue
Reduction of MIRV below 4.0 mg/kg will not be permitted. Dose re-escalation is not permitted.	

Abbreviations: AIBW = adjusted ideal body weight; MIRV = mirvetuximab soravtansine.

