5.5.3. Monitoring of Noninfectious Pneumonitis

Noninfectious pneumonitis has been observed after the administration of MIRV. Noninfectious pneumonitis may result in fatigue, shortness of breath, cough, or respiratory distress. Drug-induced pneumonitis may be immediately life threatening. If a patient presents with signs or symptoms consistent with pneumonitis and/or other clinically meaningful signs or symptoms of pulmonary toxicity, the patient should be immediately evaluated. Patients are advised to notify their treating physician immediately if they experience new or worsening shortness of breath, cough, or respiratory distress. Patients who are asymptomatic may continue dosing of MIRV with close monitoring.

The management and treatment guidelines outlined in [Table 6](#) should be followed.

Table 6: Management of Noninfectious Pneumonitis

CTCAE v5.0 Grade	CTCAE v5.0 Definition	Medical Management of Pneumonitis	Guidelines for Dose Modifications^a
Grade 1	Asymptomatic; clinical or diagnostic observations only; intervention not indicated	
 • Radiologic assessments (CT scan and/or chest x-ray) should be performed as clinically indicated. • Monitor for pulmonary symptoms. 	
 • Continue dosing in asymptomatic patients and monitor closely.
Grade 2	Symptomatic; medical intervention indicated; limiting instrumental ADL	
 • Radiologic assessments (CT scan and/or chest x-ray) should be performed as clinically indicated. • Patient must be evaluated by a pulmonary specialist. • Treatment with corticosteroids may be indicated as recommended by a pulmonary specialist and/or institutional guidelines. 	
 • Hold dosing until symptoms resolve to \leq Grade 1. • MIRV may be resumed at same dose level or one dose level lower after discussion with the Sponsor.
Grade 3	Severe symptoms; limiting self-care ADL; oxygen indicated	
 • Radiologic assessments (CT scan and/or chest x-ray) should be performed as clinically indicated. • Patient must be evaluated by a pulmonary specialist. • Treatment with corticosteroids until resolution of symptoms may be indicated as recommended by a pulmonary specialist and/or institutional guidelines. 	
 • Permanently discontinue MIRV.

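### Table 3 spares a short symptomatic Grade 3 chemistry abnormality the hold to Grade 1 and the dose cut, but not the same MIRV-related event without symptoms; *asymptomatic* was probably meant

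*Protocol*

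**What the plan says.** Table 3 in Protocol 5.5.1.1 governs MIRV-related AEs. Its last block covers all non-hematological toxicities without a row of their own. A Grade 3 event there means a hold until Grade 1 or lower, then a restart one dose level down. The block's heading lists exceptions: events due to underlying disease, Grade 3 fatigue, and "isolated symptomatic Grade 3 biochemistry laboratory abnormalities that last for < 7 days including electrolyte abnormalities that respond to medical intervention".

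An excepted event falls back on the general redosing rule in 5.5.1: "All non-hematologic toxicities for which a causal association to study drug cannot be ruled out, must be" at Grade 2 or lower, or back at baseline, with ocular disorders and pneumonitis treated separately. That rule carries no dose cut.

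Table 4 (5.5.1.2) sets the levels at 6, 5 and 4 mg/kg, with discontinuation below that, and states that "Dose re-escalation is not permitted". The electrolyte section (5.5.4) asks for prompt correction but gives no hold or dose rule. Neither it nor the discontinuation list in 5.5.6 corrects or explains the word *symptomatic*.

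**The concern.** An exemption for brief, isolated laboratory abnormalities would normally be meant for values that do the patient no evident harm. As printed, this one gives the lighter action to the patient who has symptoms and the heavier action to the patient who has none.

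It is an operative rule: 7.10 requires laboratory results to be reviewed before every dose. At stake are an avoidable, irreversible dose cut in a symptom-free patient and the loss of the stricter hold and automatic cut in a symptomatic one. Sites may also split between following the letter and following the presumed intent. SAP 6.2 tabulates related TEAEs leading to dose reduction or delay, and those descriptive tables would carry the inconsistency.

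**Working it through.** The plan states no figure to reproduce, so the check sets the rules side by side.

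**1. The two literal paths.** Take a MIRV-related, isolated Grade 3 chemistry AE lasting under 7 days.

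| | With symptoms (exempt) | Without symptoms (not exempt) |
|---|---|---|
| Rule | 5.5.1 only | Table 3 Grade 3 action |
| Redose when | Grade 2 or lower, or baseline | Grade 1 or lower |
| Dose on restart | Same level permitted | One level lower |
| Reversible | Not applicable | No (Table 4) |

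**2. Can the right-hand column contain anyone?** Yes. Under 8.1.1.1 a laboratory value is an AE if it causes signs or symptoms, or if it is clinically significant, for instance because it needs treatment. A symptom-free value that is treated can therefore qualify.

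**3. Size of the cut, from Table 4.**
- 6 to 5 mg/kg: (6 − 5)/6 = 16.7%
- 5 to 4 mg/kg: (5 − 4)/5 = 20.0%
- two such events, 6 to 4 mg/kg: (6 − 4)/6 = 33.3%
- at 4 mg/kg: discontinuation

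The symptomatic path has a mandatory cut of 0%. The hold criteria themselves part company only when the event stands at Grade 2 on the dosing day, or at a baseline above Grade 1.

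**4. Comparison with neighboring rules.**
- *Neutropenia.* Grade 3 alone resumes at the same level. "Febrile neutropenia Grade 3 or 4" resumes one level lower.
- *Thrombocytopenia.* Grade 3 alone resumes at the same level. The row for "Grade 3 associated with clinically significant bleeding that requires transfusion therapy and Grade 4" resumes one level lower.
- *Ocular (5.5.2.2).* "Treatment should not be interrupted solely for Grade 2 ocular signs" without matching symptoms, whereas Grade 2 symptoms require interruption.
- *Pneumonitis (5.5.3).* "Patients who are asymptomatic may continue dosing of MIRV with close monitoring", while symptomatic Grade 2 is held. This is weaker evidence, because Table 6 defines Grade 1 as asymptomatic and Grade 2 as symptomatic. The split is by grade, not within one.
- *Grade 3 fatigue.* It is exempted in the same heading as the disputed words, although it is itself a symptom. This points the other way.

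So three rules separate events of the same grade by symptom or clinical consequence, and all three are stricter when it is present. The chemistry exemption is the reverse.

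**5. Effect of substituting *asymptomatic*.** The two columns in step 1 swap, and the milder event gets the lighter action.

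**The case against.** The strongest reply is that few patients meet the rule on either side.

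- *Symptomatic side.* Section 8.1.1.1 has laboratory AEs recorded under the associated sign, symptom or diagnosis. A symptomatic abnormality may then be handled under that term's own row. The requirement that the event be isolated also sits awkwardly with symptoms. Dosing is every 3 weeks, so an event under 7 days will often have improved by the next dose.
- *Symptom-free side.* The value must qualify as an AE and be MIRV-related. The closing electrolyte clause can be read as exempting treated electrolyte events whether or not they cause symptoms, and electrolytes are the chemistry class that 5.5.4 singles out.

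These points stand and limit the reach. They do not remove the reversal: the electrolyte clause cannot help for other chemistry tests, and the cut applies even when the value has recovered before the next dose.

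Investigator judgment is a partial answer. The exemption permits same-dose redosing without requiring it, and 5.6.1 lets the investigator stop treatment at any time. Judgment does not relieve the symptom-free patient of the mandatory cut, since 12.7 requires adherence and rules out prospective waivers.

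A reader might infer that the symptomatic patient is left with no protection. The text does not support that: 5.5.1 still requires Grade 2 or lower or baseline, and Grade 4 events and Grade 3 or higher cardiac events (other than Grade 3 hypertension) still mean discontinuation. A reader might also infer that the protocol is otherwise uniformly stricter when symptoms are present. The fatigue exemption and the grade-defined pneumonitis split do not bear that out.

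**Conclusion.** The literal reversal is in the text and nothing elsewhere corrects it. It should be fixed because it governs dosing, but it is not a critical flaw. Per affected patient the difference is no mandatory cut against an irreversible cut of 16.7% or 20%, or discontinuation at 4 mg/kg.

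The documents give no frequency for these events, so no trial-level size can be estimated. For scale only, one patient among about 110 treated is 1/110 = 0.9 percentage points of the related dose-reduction rate.

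That *asymptomatic* was intended is an inference from the comparable rules; the documents do not confirm it. The conclusion also assumes that the issued protocol page carries the word as quoted, which is worth checking first. It would be wrong to go further and infer harm to the efficacy results: nothing in the documents shows an effect on ORR, DOR or power.

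**What to change.** Ask the sponsor's medical team to confirm the intent. If confirmed, change *symptomatic* to *asymptomatic* in the Table 3 exemption by protocol amendment under 12.7.

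In the same step the team should decide whether liver tests (ALT, AST, total bilirubin, alkaline phosphatase) and creatinine stay outside the exemption. The one-word change would otherwise loosen the current rule for short asymptomatic Grade 3 values of these tests, allowing redosing at the same level from Grade 2. The row already shows hepatic caution: "For any Grade 3 hepatic toxicity that does not resolve to baseline within seven days, an abdominal CT scan must be performed". This is a medical choice, not a statistical one. It would also help to say whether the electrolyte clause covers symptomatic events, since changing one word leaves that open.

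The cost is an amendment with written ethics approval across about 98 centers, though 12.7 allows expedited review of minor changes. No procedures or patients are added. The clinical downside is that short symptomatic Grade 3 chemistry events would then be held and dose-reduced.
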